Title: Tamsulosin and Time to Spontaneous Void Following Hysterectomy: A Randomized Controlled Trial

Authors: [name] MD, [name] MD, [name] MD, [name] MD, [name] MD, [name] MD, [name] MD, [name] MD

NCT number: NCT04859660

Date of document: 7/19/2023

Protocol

The study was a double-blinded, placebo- controlled randomized control trial that took place at two tertiary care hospital campuses in Tucson, Arizona, between June 2021 and January 2023 and involved 11 attending surgeons. Approval from the institutional review board and registration on ClinicalTrials.gov was obtained prior to enrollment.

Women 18-80 undergoing minimally invasive hysterectomy for benign indications were screened for participation. In this study, minimally invasive hysterectomy included the following procedures: total vaginal hysterectomy (TVH), total laparoscopic hysterectomy (TLH), laparoscopic assisted vaginal hysterectomy (LAVH), robotic assisted laparoscopic hysterectomy (RA-TLH), Vaginal Natural Orifice Transluminal Endoscopic Surgery (vNOTES), and supracervical hysterectomy. Patients were excluded from analysis if they had a planned concurrent incontinence surgery (e.g. colporrhaphy, vaginal vault suspension or sling procedure), a history of bladder cancer, or a medical contraindication to tamsulosin. Participants requiring Foley catheterization due to complications such as bladder injury were excluded. Patients were screened and consented a week prior to their scheduled surgery. The day of surgery, either 0.4mg tamsulosin or placebo was administered on average 1 hour before surgery. This timing was chosen because the peak plasma concentration of tamsulosin occurs at 4 hours, so taking into account the total operating room (OR) time (from rolling to the OR to leaving the OR suite) the medication onset coincides with the patient arriving to the PACU. Randomization was performed by the hospital investigational pharmacy, who dispensed the study medication or placebo in a blinded fashion. Both tamsulosin and placebo study medication were encapsulated and were indistinguishable from one another.

Each participant underwent a void trial post-operatively by backfilling their bladder with 200cc normal saline at the conclusion of the case and removing the foley. Demographics, medical and surgical history, surgical details, PACU discharge time, time to void, and adverse events were recorded. Adverse events included intraoperative complications, rate of readmission, and emergency department visits.

Statistical Analysis Plan

The study aimed to examine two primary objectives: (1) the time to void in the tamsulosin intervention group compared to the placebo group, and (2) the time to discharge from the PACU. A reduction of at least thirty minutes in time to void was considered a significant change that could alter the standard of care. Based on Chao et al, the time to void following a backfill void trial is 181 minutes. To determine if tamsulosin results in a 30 minute decrease in time to post-operative void, a total of 77 participants per group were needed, assuming a 5% significance level and 80% power. To account for 10% drop out or exclusion, a total of 170 patients (85 per group allocation) were consented. Wilcoxon rank-sum test was used for continuous variables and Fisher's exact test was used for categorical variables. A P value of <0.05 was considered statistically significant.

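### No named adverse event covers reactions to the capsule or the PACU stay, the window the dosing was timed to reach, so PACU tolerability cannot be compared between arms

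*Combined protocol and SAP*

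**What the plan says.** The last paragraph of the Protocol section lists what was collected: "Demographics, medical and surgical history, surgical details, PACU discharge time, time to void, and adverse events were recorded". The next sentence expands the last item: "Adverse events included intraoperative complications, rate of readmission, and emergency department visits". No definitions, time window or grading follow.

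Earlier in the same section, "either 0.4mg tamsulosin or placebo was administered on average 1 hour before surgery". The reason given is that "the peak plasma concentration of tamsulosin occurs at 4 hours", so that, allowing for OR time, "the medication onset coincides with the patient arriving to the PACU". The only other drug-safety text is the exclusion for "a medical contraindication to tamsulosin", which is not specified further.

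The Statistical Analysis Plan names time to void and time to PACU discharge as the two primary objectives. On the first it states: "A reduction of at least thirty minutes in time to void was considered a significant change that could alter the standard of care". It assigns Fisher's exact test to categorical variables in general and names no adverse-event comparison.

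**The concern.** The design aims the drug's action at the PACU and measures both primary outcomes around that stay, but names no harm outcome there. One listed harm is confined to the operation; the other two are later hospital use.

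At stake is what the trial can say about tolerability. The plan treats a saving of 30 minutes as enough to alter care. A reader deciding whether to adopt the drug on that basis will want to know how it was tolerated. A finding of no difference in the listed events would rest on outcomes not chosen to show the drug's effects. A mild or moderate reaction in the PACU could occur more often on tamsulosin and appear in no table.

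**Working it through.** **Step 1. Set the named outcomes against the timeline.** All entries come from the Protocol section, except the primary objectives, which come from the Statistical Analysis Plan.

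- Capsule to OR (on average 1 hour): no adverse event named.
- In the OR: intraoperative complications, undefined.
- Leaving the OR to discharge: no adverse event named. Both primary outcomes are measured around this period.
- After discharge: readmission and emergency department visits.

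**Step 2. Where does the plasma peak fall?** The peak is at 4 hours and dosing is on average 1 hour before surgery, so the peak comes about 4 − 1 = 3 hours after surgery starts. OR time is not given. An OR time near 3 hours puts the peak at PACU arrival, a shorter one puts it after arrival, and a longer one puts it in the OR. The text itself says that onset coincides with arrival. That the peak also falls at or near arrival is a fair inference from the stated rationale, not the protocol's own statement.

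**Step 3. Is there a figure in the plan to reproduce?** Not on this point. The sample size (77 per group, 85 after the allowance for drop-out or exclusion) is for time to void and is not in dispute here. It serves below only as the number of patients available.

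**Step 4. What could captured PACU reactions show?**

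Zero events: the upper limit of the exact two-sided 95% interval for 0 of n is 1 − 0.025^(1/n).

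- n = 77 (the number needed): 1 − 0.025^(1/77) = 4.7%.
- n = 85 (the number allocated, and so the most who could be dosed per group): 1 − 0.025^(1/85) = 4.2%.

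Comparison between arms: power of Fisher's exact test, two-sided 0.05, 77 per group, found by summing the joint binomial probabilities of all pairs of counts with p < 0.05. The documents give no event rates, so these are assumed.

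- 5% v 20%: 0.774
- 5% v 15%: 0.459
- 5% v 10%: 0.134

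Precision: for 5% v 10% with 85 per group, the approximate 95% half-width for the risk difference is 1.96 × √(0.05 × 0.95/85 + 0.10 × 0.90/85) = 1.96 × 0.0402 = 7.9 percentage points, around a difference of 5.

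So recording these events would bound common reactions and show a large excess. It would not reliably detect a doubling.

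**The case against.** The strongest reply has four parts.

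**The list may not be complete.** The text says that adverse events were recorded and that they included three kinds. The document is a short, past-tense summary dated after the trial ended. A reader might infer that no PACU reactions were collected. The text does not support that; it supports only that none is named. This stands, and it is why the fix starts by asking what was recorded. But a plan can be judged only on the outcomes it names.

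**Harm is not wholly unmeasured.** A reader might infer that harm cannot be weighed at all. That goes too far. A reaction leading to readmission or an emergency visit is counted. Intraoperative complications are undefined and might take in haemodynamic events in the OR. A reaction that prolongs the PACU stay already enters the second primary outcome in a blinded, randomised comparison. What is missing is identification of reactions in the PACU, chiefly the milder ones. For the same reason, the gap does not bias the PACU discharge estimate.

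**The protocol does not say that exposure peaks in the PACU, or that every patient should receive the drug.** Both might be inferred. The first is reasonable but is not stated; the second has no basis beyond the remark about altering the standard of care.

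**A Fisher comparison would be weak.** This also stands: power is below 50% for a threefold difference from 5%, all rates are assumed, and the documents name no specific tamsulosin reaction. It argues for descriptive reporting with intervals rather than for leaving the window empty.

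**Conclusion.** The point holds in limited form. The named adverse events contain no reaction to the capsule and nothing between leaving the OR and discharge, although dosing was timed so that onset meets PACU arrival. As written, PACU tolerability cannot be compared between arms, and no difference in the listed events would be little evidence about the drug.

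The time-to-void and PACU-discharge comparisons, the sample size and the error rate are unaffected. The matter is worth correcting because it changes what may be concluded about tolerability at small cost. The conclusion assumes that the three named kinds are the full set analysed; if PACU events were in fact recorded, the remaining task is to define and report them.

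**What to change.** 1. State whether events in the PACU were recorded and, if so, with what definitions and over what period.
2. Extend the adverse-event definition to any event from capsule administration to PACU discharge, abstracted from existing anaesthesia and PACU charts by someone blind to arm.
3. Fix the categories before abstraction. Treated low blood pressure and dizziness or fainting are suggestions, since the documents list none; the investigators should settle the list.
4. Report catheter reinsertion separately, as a voiding outcome. It mainly reflects failure to void and does not fill the drug-reaction gap.
5. Give counts by arm among all dosed patients (up to 85 per group) with a confidence interval for the risk difference. Fisher's exact test, already in the plan, may be shown, but the table should be labelled descriptive and a non-significant result not read as equal tolerability.
6. If the charts cannot support this, draw no tolerability conclusion and state the limitation.

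The cost is modest abstraction time and one safety table. No visit, procedure or aspect of treatment changes. Because enrolment has ended, completeness depends on what was charted in routine care, and the report should say so.

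### Two primary objectives share one unadjusted P<0.05 threshold and this document states no decision rule; if either may carry a primary claim, family-wise error exceeds 5% (9.75% if independent, never above 10%)

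*Combined protocol and SAP*

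**What the plan says.** The Statistical Analysis Plan opens with "The study aimed to examine two primary objectives: (1) the time to void in the tamsulosin intervention group", compared with placebo, "and (2) the time to discharge from the PACU". Both are called primary. The only criterion for significance, placed at the end of the section after the list of tests, is "A P value of <0.05 was considered statistically significant".

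The two objectives are not specified to the same depth. For time to void the plan gives a threshold of importance, "A reduction of at least thirty minutes in time to void was considered a significant change that could alter the standard of care", and a sample size, "To determine if tamsulosin results in a 30 minute decrease in time to post-operative void, a total of 77 participants per group were needed". Time to void is also the outcome in the trial's title. PACU discharge time has no target difference and no power statement.

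Neither the Protocol section nor the Statistical Analysis Plan says how the two primary results combine into a conclusion. Two other facts bear on the point. The title block reads "Date of document: 7/19/2023", while the Protocol section places the trial "between June 2021 and January 2023". The Protocol section also says that "registration on ClinicalTrials.gov was obtained prior to enrollment".

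**The concern.** With two primary objectives, a plan has to say what counts as success: both, either, or one tested before the other. The family-wise error rate depends on that choice, and this document does not state it.

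The case left open is a null result on time to void together with P<0.05 on PACU discharge. Applied literally, the stated threshold lets that be reported as a positive primary finding. Such a claim would have two weaknesses. The 5% level would not hold across the two declared primaries, and the claim would rest on an endpoint for which the plan sets no meaningful difference and no power. The other outcomes are less exposed: a positive time to void was tested at 5% in any case.

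**Working it through.** **Inputs.** From the Statistical Analysis Plan: two primary objectives, a threshold of 0.05 for each, 77 per group, a 30-minute difference, 80% power, and the Wilcoxon rank-sum test for continuous variables. Assumed: two-sided tests (the plan does not state sidedness) and a correlation *r* between the two test statistics (the documents give none, so a range is shown).

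**The plan's own figure.** The 77 per group cannot be reproduced, because no standard deviation is given. It can be solved backwards from n = 2·SD²·(1.960 + 0.842)²/30²:

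- SD = 66.1 gives 76.2, which rounds up to 77.
- SD = 66.4 gives 76.9, which rounds up to 77.

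The implied SD is therefore about 66 minutes. It is used only for the cost of an alpha split, below. The error-rate calculation does not depend on it.

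**Family-wise error if either result suffices, both nulls true.**

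- Independent tests: 1 − (1 − 0.05)² = 1 − 0.9025 = 0.0975.
- Bound under any dependence: 0.05 + 0.05 = 0.10.
- Correlated tests: 1 − P(|Z₁| ≤ 1.96 and |Z₂| ≤ 1.96), with Z₁ and Z₂ bivariate normal with correlation *r*.

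Time to void alone already uses 0.05, so the excess is the probability of a false PACU-only result, P(PACU significant, time to void not) = family-wise error − 0.05.

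| Assumed *r* | Family-wise error | False PACU-only result |
|---|---|---|
| 0 | 9.75% | 4.75 points |
| 0.5 | 9.07% | 4.07 points |
| 0.8 | 7.81% | 2.81 points |
| 0.9 | 7.04% | 2.04 points |
| 1 | 5.00% | 0 |

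A simulation of the planned test (77 per group, Wilcoxon rank-sum with normal approximation, 100,000 trials per setting, patient-level correlations 0, 0.5, 0.8 and 0.9) gave 9.80%, 9.20%, 8.03% and 7.10%. The normal calculation is therefore adequate here.

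**Other decision rules.**

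- Time to void first, PACU discharge tested only if it is significant: at most 5%. With both nulls true, a false claim requires time to void to reject, which has probability 0.05.
- Both must succeed: at most 5%, reached when one null is true and the other effect is large. With both nulls true and independent tests it is 0.05 × 0.05 = 0.25%.
- Bonferroni, 0.025 each: at most 5%, and 1 − 0.975² = 4.94% if independent.

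**Cost of Bonferroni for time to void.** Take SD = 66.4 and 77 per group. The standardised effect is 30/(66.4 × √(2/77)) = 2.80. Power at 0.05 is Φ(2.80 − 1.96) = 80%. At 0.025 it is Φ(2.80 − 2.24) = 71%. Restoring 80% would need about 77 × 1.211 = 93.2, that is 93 to 94 per group across the implied SD range.

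**The case against.** The strongest reply is that time to void is the real primary endpoint. It is in the title, and it has the only target difference and the only sample size. A rule under which PACU discharge alone suffices is the reading that the text supports least. That is fair, and it limits the point to an unstated rule rather than demonstrated inflation. It does not dispose of it: the plan still calls both objectives primary and nowhere makes PACU discharge secondary or conditional. Emphasis is not a testing order.

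Second, this is a short past-tense summary dated after the trial ended, and the trial was registered before enrollment. A reader might infer that no rule was ever set in advance. The documents do not support that. They show only that none is stated here.

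Third, 10% is a bound, and 9.75% assumes independence. Both times are measured in the same patients after the same operation, so positive correlation is plausible and would bring the figure down. This stands as a caution on size. The excess shrinks with correlation but disappears only at a correlation of 1.

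Fourth, barring a stand-alone PACU claim amounts to a gatekeeping order chosen after the trial, whereas Bonferroni or Holm would treat the two primaries alike. This also stands, and has to be acknowledged when the limit is applied.

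**Conclusion.** The plan is wrong as written on a condition: that a positive result on either objective may support a primary claim, a reading that the text does not exclude. On that condition, with both nulls true and two-sided tests, family-wise error is above 5% for any correlation below 1. It runs from about 7.0% at an assumed 0.9 to 9.75% under independence, with 10% as the ceiling. If both must succeed, or time to void is tested first as a gate, it is at most 5%.

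Two stronger readings are tempting and unsupported. One is that the trial's error rate is 10%; that is a limit, and it applies only under a rule that the plan does not adopt. The other is that the time-to-void comparison is compromised; its own test at 5% is untouched.

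The consequence is confined to a positive result on PACU discharge alone. The point should be fixed, but it sits at the low end of that grade.

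**What to change.** Check for a record, made before unblinding, of how the two primary results were to be combined; the registration is an obvious place to look. If there is one, state that rule, whatever it is, with its date, and apply it.

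If there is none, disclose that the two primary tests were unadjusted, report each with an estimate and 95% confidence interval, and make no confirmatory claim on PACU discharge alone.

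This needs no extra patients, no change of test and no loss of alpha for time to void. The cost should be stated openly: PACU discharge keeps its primary label but loses independent confirmatory standing, and that limit is imposed after the trial.

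Bonferroni or Holm is a symmetric alternative that also holds 5%, though without a prior record it too would be a choice made after the trial. Bonferroni would leave time to void with about 71% power at 77 per group, under the back-solved SD of about 66 minutes. Holm would never do worse than that, since it relaxes to 0.05 for time to void when PACU discharge is significant at 0.025.

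### Does consenting 85 per group fail to protect the 77 per group that the sample size calculation requires?

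*Combined protocol and SAP*

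**What the plan says.** The sample size text is in the Statistical Analysis Plan. It takes from an earlier published study that "the time to void following a backfill void trial is 181 minutes", treats a 30-minute reduction as the difference worth detecting, and states "a total of 77 participants per group were needed, assuming a 5% significance level and 80% power". It then allows for loss: "To account for 10% drop out or exclusion, a total of 170 patients (85 per group allocation) were consented". It does not show how the allowance was calculated, and it gives neither a standard deviation nor the sidedness of the test. Continuous outcomes are to be compared by the Wilcoxon rank-sum test.

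The Protocol section adds the timing: "Patients were screened and consented a week prior to their scheduled surgery". It also lists reasons for exclusion that can arise after enrolment, such as a bladder injury that requires a catheter.

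**The concern.** An allowance for loss is normally obtained by dividing the required number by the proportion expected to remain. Multiplying by one plus the loss rate is a common slip and always gives too few. Here 77 × 1.10 = 84.7 rounds up to 85, which is the plan's figure, so the slip appears to have been made. A 10% loss then leaves fewer than the plan says it needs, and the two adjacent sentences seem to disagree.

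Two features add to the suspicion. The 170 are counted at consent, about a week before dosing, so cancellations and withdrawals before surgery draw on the same margin as later exclusions. And 77 cannot be checked independently without a standard deviation, so one looks harder at whether the margin above it is sound. If the margin really fell short, the trial would have less than its stated power for time to void.

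**Working it through.** **Inputs, all from the Statistical Analysis Plan:** 77 required per group; 10% allowance; 85 per group and 170 in total consented; 5% significance level; 80% power; 30-minute difference. Two-sided testing is assumed because sidedness is not stated.

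**1. Reproducing the 85.**
- Multiplying: 77 × 1.10 = 84.7, rounded up to 85.
- Dividing: 77 / 0.90 = 85.56, which is 85 rounded down or 86 rounded up.

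Both routes can reach 85, so the figure does not show which was used.

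**2. What remains after a 10% loss.**
- Per group: 85 × 0.90 = 76.5, against 77.
- In total: 170 × 0.90 = 153, against 154.
- Largest loss that keeps 77 per group: (85 − 77) / 85 = 8/85 = 9.4%.
- Number that fully covers 10%: 86 per group, 172 in total.

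The gap in patients to be consented is one per group. The gap in evaluable patients, which is what determines power, is half a patient per group.

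**3. Effect on power.** With difference δ, standard deviation σ and n per group, the normal approximation is power = Φ(δ / (σ√(2/n)) − 1.960). If 77 per group gives exactly 80%, then δ / (σ√(2/77)) = 1.960 + 0.842 = 2.802. At 76.5 per group this becomes 2.802 × √(76.5/77) = 2.792, and power = Φ(2.792 − 1.960) = Φ(0.832) = 79.7%.

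The standard deviation cancels once 77 is tied to 80%, so its absence hardly affects this step. Variants:

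| Case | Power |
|---|---|
| Two-sided t-test, 76.5 per group | 79.7% |
| Rank-sum, scaled by its relative efficiency, 76.5 per group | 79.7% |
| One-sided normal, 76.5 per group | 79.8% |
| Two-sided t-test, 76 per group | 79.5% |
| Two-sided t-test, 76.5 per group, where 77 was itself rounded up from 76.03 (SD 65.6) | 80.2% |

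The loss is about 0.3 percentage points at most for 76.5 per group, and it vanishes if 77 had been rounded up from just over 76.

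**4. Scale against chance.** If each of 85 patients is lost independently with probability 0.10, the number lost has mean 8.5 and standard deviation √(85 × 0.10 × 0.90) = 2.77. Half a patient is 0.5 / 2.77 = 0.18 of that standard deviation. Ordinary variation in dropout is much larger than the discrepancy.

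**The case for a change.** The strongest case for a correction is that the headcount mismatch is certain, needs no outside figure, and would cost one sentence to put right: 170 covers up to 9.4% loss. Any reader who divides by 0.90 will see it. That stands as arithmetic. It does not show that planned power was lost, and it contradicts the plan only if the 10% is read as a share of those enrolled. An addition of 8 to 77 is 8/77 = 10.4% of the required number, and the plan's wording does not exclude that reading, although a share of those enrolled is the better convention.

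A second argument is that counting from consent leaves no separate margin for cancellations before surgery. But the plan ties one allowance, for dropout and exclusion together, to the number consented. Losses before dosing are within its scope. Nothing in the documents suggests that the 10% was meant only for losses after dosing.

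A third argument concerns the missing standard deviation, and it has substance. Under assumed values and a two-sided t-test, power at 77 per group is 87% for 60 minutes, 69% for 75 and 54% for 90. These differences dwarf the 0.3 points at issue. They concern the origin of the 77, however, and not the step from 77 to 85. A value recovered by working backwards (about 66 minutes two-sided, about 75 one-sided) only restates the 77 and is no evidence of what was assumed.

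**Conclusion.** No change follows, because a correction would gain nothing. Strictly, 85 per group covers a 9.4% loss and 86 would be needed for a full 10%. The consequence is half an evaluable patient per group and power of about 80%, as planned. This rests on 77 per group being right for 80% power, on equal allocation, and on a loss of exactly 10%. The documents do not report the actual loss, so no real shortfall has been shown.

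That a wrong formula was used remains an inference, since a rounding choice explains the 85 equally well. The Protocol describes a trial run from June 2021 to January 2023 in a document dated July 2023, so the number consented is already settled. Restating the allowance as 9.4% would leave the design, the analysis and the interpretation of the result as they are.

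### The rank-sum analysis of time to void, a primary endpoint, has no rule for a participant who does not void; anyone without a recorded time would drop out of the comparison

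*Combined protocol and SAP*

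**What the plan says.** The Statistical Analysis Plan section opens with the objectives: "The study aimed to examine two primary objectives: (1) the time to void in the tamsulosin intervention group compared to the placebo group", followed by time to discharge from the PACU. The title words the outcome more narrowly: "Tamsulosin and Time to Spontaneous Void Following Hysterectomy".

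The Protocol section says how the outcome arises: "Each participant underwent a void trial post-operatively by backfilling their bladder with 200cc normal saline", after which the Foley is removed. It gives no time limit for the trial and does not define failure.

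On data collection it says "Demographics, medical and surgical history, surgical details, PACU discharge time, time to void, and adverse events were recorded" and "Adverse events included intraoperative complications, rate of readmission, and emergency department visits". Neither list names void-trial failure, urinary retention or re-catheterisation.

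The one analysis sentence that reaches time to void is "Wilcoxon rank-sum test was used for continuous variables". No censoring rule, assigned rank, time-to-event method or missing-data rule goes with it. The nearest related text is an exclusion in the Protocol section: "Participants requiring Foley catheterization due to complications such as bladder injury were excluded".

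**The concern.** A rank-sum test uses only participants who have a value. With no rule for a participant who does not void, a blank time removes her without comment. If that happens, the comparison is no longer between the groups as randomised. It is between those in each arm who voided, and whether a participant voids is something the drug may change.

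The worst outcomes would then be missing from a primary comparison. If tamsulosin reduced retention it would get no credit, and if it increased retention that would not count against it. Because failure is not in the listed data, a reader also cannot tell a blank that means a failed trial from one that means a lost record.

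**Working it through.** **Step 1. Follow each kind of participant through the plan as written.**

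| Participant | What the plan's test does |
|---|---|
| Voids, time recorded | Ranked |
| Re-catheterised, voids later, time recorded | Ranked, probably among the longest times |
| Does not void, no time recorded | No rule; drops out |
| Voided, but the time was not recorded | No rule; drops out, and looks the same as the row above |
| Removed under the Foley exclusion | Not analysed; the text does not say whether a failed void trial counts |

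**Step 2. Look for other text that fills the gap.**

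- *Foley exclusion.* Its example is bladder injury, so it most naturally means surgical complications. If it did cover failed trials, non-voiders would be removed by rule after randomisation, which does not cure the problem.
- *The 10% allowance.* 77 × 1.1 = 84.7, rounded to 85 per group, or 170 in all. This replaces numbers. It does not assign an outcome to anyone.
- *Other outcomes.* PACU discharge time, readmissions and emergency visits may partly reflect retention. None counts failed void trials.

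None of these gives a non-voider a value or rank.

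**Step 3. The plan's own figure.** The 77 per group cannot be reproduced, because no SD is given. Solving backwards:

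SD = Δ√(n/2) / (z₁₋α/₂ + z₀.₈₀) = 30 × √38.5 / (1.960 + 0.842) = 186.1 / 2.802 ≈ 66.4 minutes (two-sided).

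With a one-sided 5% level the divisor is 1.645 + 0.842 = 2.487, giving 74.9 minutes. The omission does not depend on this figure; the SD only sets the scale for the simulation in Step 5.

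**Step 4. Illustration by formula.** Assume times among voiders have the same distribution in both arms, and that proportions p_T (tamsulosin) and p_P (placebo) do not void. With non-voiders tied at the worst rank, the probability that a tamsulosin participant does better than a placebo participant, counting ties as half, is

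θ = ½(1−p_T)(1−p_P) + (1−p_T)p_P + ½p_T·p_P = ½ + (p_P − p_T)/2.

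Take p_T = 5% and p_P = 20%, which are assumed rates: θ = 0.380 + 0.190 + 0.005 = 0.575. With 77 per group the null standard error is √[(2n+1)/(12n²)] = √(155/71,148) = 0.0467. Then 0.075/0.0467 = 1.61, and the chance of significance is about Φ(1.61 − 1.96) = Φ(−0.35) ≈ 36%. With non-voiders dropped θ is exactly 0.5, and the chance is the 5% error rate. A simulation of 4,000 trials gave 38% and 6%; a longer check gave 36% and 5%.

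**Step 5. Illustration by simulation.** Assumptions: 77 per group, lognormal times, SD 66.4, means 151 and 181 minutes (181 − 30 = 151), failure unrelated to a participant's own speed, two-sided 5%, 4,000 trials per row (simulation error at most about 0.8 points).

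| Not voiding, tamsulosin / placebo | Significant, non-voiders dropped | Significant, worst rank |
|---|---|---|
| 0% / 0% | 90% | 90% |
| 10% / 10% | 85% | 73% |
| 5% / 15% | 85% | 95% |
| 15% / 5% | 85% | 32% |

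The dropped column stays at 85% in the last three rows: the voiders-only test does not respond to which arm had more retention. The 10% / 10% row shows the price of worst rank when failure has nothing to do with treatment.

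If instead the slowest participants are the ones who fail, the two approaches differ less. With 85 per arm, a true 30-minute reduction and 10% placebo failure, dropped versus worst rank is 88% versus 91% (lognormal, additive shift), 79% versus 90% (lognormal, proportional shift) and 69% versus 82% (normal). At 2% to 5% failure under the additive lognormal the difference is under one point.

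**The case against.** The strongest reply is that the harm needs two facts the documents do not supply: that someone failed the void trial, and that she had no recorded time. Time to void is listed as recorded and no cut-off is set, so a late voider, even one who was re-catheterised, may have a time and already sit among the worst ranks. The word spontaneous appears only in the title; the objective and the sample-size sentence do not use it. All of this stands, and it is why the point is conditional.

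A reader might infer that non-voiders were in fact left out, or that the result is biased for or against tamsulosin. The documents support neither reading: they report no failures, no blanks and no counts by arm. Nor does the silence of the data list prove that failure was never recorded.

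It is also fair to say that the power figures rest wholly on assumed rates, mechanism and distribution, and that worst rank mixes speed with failure and can cost more power than it gains. Both objections stand. They argue against resting the point on the simulations, and against putting worst rank in place of the planned test.

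What does not stand is that the Foley exclusion, the 10% allowance or the other outcomes close the gap. The possibility that everyone voided does not close it either: reporting zero in each arm would settle the matter, but the present text does not do so.

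**Conclusion.** The point holds in conditional form and should be fixed. It is certain from the text that a primary endpoint, measured through a trial that can be failed, has no value or rank for failure, and that failure is not in the listed data or adverse events. It follows that any participant without a time is dropped and the comparison is confined to voiders.

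Whether this happened, to how many and in which direction is unknown. If nobody failed, or all who failed later had a time recorded, the consequence is nil. If failure was uncommon and confined to the slowest, it may be slight. If failure differed between the arms, the planned test could miss it entirely. The calculations show only that the missing rule can matter. They do not estimate its effect in this trial.

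**What to change.** The trial is complete, so all of this should be labelled post hoc.

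1. Report, by arm, how many participants failed the void trial or have no recorded time, including any removed under the Foley exclusion. Separate failed trials from lost records where possible, and state how a participant who was re-catheterised and voided later was classed. Compare the arms with the Fisher's exact test already planned.
2. Keep the planned rank-sum result as the main analysis. Beside it, as a sensitivity analysis, repeat the test on all randomised participants who had the void trial, with non-voiders tied at a rank worse than the longest observed time.
3. If the two disagree, limit the conclusion to time to void among those who voided.

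The cost is a small reanalysis with no new participants. It needs failure by arm to be retrievable, which the documents do not state; if it is not, that should be reported as a limitation. Worst rank loses power when failure is unrelated to treatment (85% to 73% in the 10% / 10% illustration), which is why it is proposed as a sensitivity analysis and not as a replacement.
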